# 12.1 Data Integrity

Data collection and storage will be inspected throughout the study by internal monitoring (performed by the Oxford Vaccine Group). The Sponsor may also audit the trial data.

# 12.2 Data Archiving and Storage

Study data will be stored electronically on a secure server, and paper notes will be kept in a secure location at the study site(s). All essential documents, which includes research data and identifiable information, will be retained for a minimum of 5 years after the study has finished. The need to store study data for longer in relation to licensing of the vaccine will be subject to ongoing review. For effective vaccines that may be licensed, we may store de-identified research data securely at the site

RECRef: 23/SC/0268 NIV001: A study of a new vaccine against Nipah IRAS project ID: 1007433 Virus in adults aged 18 to 55

Page 52 of 71

at least 99 years after the end of the study, subject to adjustments in clinical trials regulations. Participants' bank details will be stored for a minimum of 7 years in line with the site financial policy. Volunteers who complete online screening or telephone screening only (before informed consent) will not have data kept beyond the end of the trial.

#### 12.3 Source Data

Source documents are original documents, data, and records from which participants' eCRF data are populated. These include, but are not limited to, hospital or GP records (from which medical history and previous and concurrent medication may be summarised into the eCRF), clinical and office charts, laboratory and pharmacy records, diaries, microfiches, radiographs, and correspondence. In this study, eCRF entries will be considered source data where it is the site of the original recording. All documents will be stored safely under strict confidentiality and with restricted access. On all study-specific documents, other than the signed consent and the participant contact sheet, the participant will be referred to by the study participant number/code only.

#### 12.4 Access to Data

Direct access will be granted to authorised representatives from the Sponsor/host institution and the regulatory authorities to permit trial-related monitoring, audits and inspections.

#### 12.5 Data Recording and Record Keeping

All study data will be recorded directly into eCRFs within an Electronic Data Capture (EDC) system (e.g. REDCap) or onto a paper source document (for later entry into the EDC system if direct entry is not available). Any additional information that needs recording but is not relevant for the eCRF (such as signed consent forms) will be recorded on a separate paper source document. All documents will be stored safely and securely in confidential conditions.

The EDC system (eCRF data) uses a relational database (MySQL/ PostgreSQL) via a secure web interface with data checks applied during data entry to ensure data quality. The database includes a complete suite of features which are compliant with GCP, EU and UK regulations and Sponsor security policies, including a full audit trail, user-based privileges, and integration with the institutional LDAP server. The MySQL and PostgreSQL database and the webserver will both be housed on secure servers maintained by Oxford Vaccine Group IT personal and local site IT personal. The servers are in a physically secure location in the UK and data are backed up on secure servers operated by the University of Oxford IT Services physically located in the UK. Backups will be stored in accordance with the IT department schedule of daily, weekly, and monthly retained for one month, three months, and six months, respectively. The IT servers provide a stable, secure, well-maintained, and high-capacity data storage environment. REDCap is widely-used, powerful, reliable, well-supported system. Access to the study's database will be restricted to the members of the study team by username and password.

The study team will use names and contact details to contact participants about the research study, and make sure that relevant information about the study is recorded for their care, in relation to their health during the study and to oversee the quality of the study. At the completion of the study, unless participants consent otherwise (e.g. requesting to be informed of other trials), participant's personal details will not be used to contact them other than exceptional circumstances concerning their safety. If consent is provided by participants to take part in another study carried out by the study site,

RECRef: 23/SC/0268 NIV001: A study of a new vaccine against Nipah Page 53 of 71

personal information and medical information including blood test results may be accessed to avoid unnecessary repetition. If participants provide specific consent, we will use personal identifiable data to invite participants for future research.

#### 13 STATISTICS

#### 13.1 Study Analyses

# 13.1.1 Descriptive Statistical Methods

The analyses for this study will be descriptive in purpose and will not include any hypothesis testing, power calculations, or presentation of p-values for group comparisons.

Counts and percentages of local and systemic solicited adverse reactions from eDiaries during days 0-6 following each vaccination will be presented for each group. Unsolicited AEs occurring during days 0-27 following each vaccination, and all SAEs and AESIs occurring throughout the duration of the study will be summarised.

Highly skewed antibody and cellular response data will be log-transformed prior to analysis. The geometric mean titres (GMTs) and associated 95% confidence intervals (CIs) will be summarised by computing the anti-log of the mean of the log-transformed data. Medians and interquartile ranges of the untransformed data may additionally be presented.

Due to the descriptive nature of the trial, no testing will be performed between groups.

# 13.1.2 The Number of Participants

Fifty-one participants will be enrolled into the study, allocated to Cohorts 1 or 2. Participants are only considered enrolled once they receive the first dose of vaccine. Recruitment will continue until fifty-one participants are enrolled.

There has been no power calculation to determine these numbers, as the study is descriptive. The sample size was chosen in line with the primary objective of providing adequate descriptive safety information to permit further evaluation in larger clinical trials. A total of 20 participants per vaccine schedule (groups 1 and 2) was deemed sufficient for a first-in-human phase I trial. With 46 participants receiving at least one dose of ChAdOx1 NipahB vaccine, the probability of observing at least one participant with an adverse event will be more than 90% if the underlying incident rate is 5%.

# 13.1.3 The Level of Statistical Significance

Any statistical significance testing will not be testing any hypotheses, but will be purely descriptive and hypothesis generating. All confidence intervals for descriptive analyses will be set at 95%.

# 13.1.4 Criteria For Termination of the Trial

The CI and DSMC will have the right to terminate the study at any time on grounds of participant safety. If the study is prematurely terminated the Investigator will promptly inform the participants and will ensure appropriate therapy and follow-up. If the study is halted, the MHRA and relevant Ethics Committee will be notified within 15 days of this occurring.

RECRef: 23/SC/0268 NIV001: A study of a new vaccine against Nipah Page 54 of 71

In the event of the trial being terminated early, follow-up of enrolled participants will still continue as planned for safety reasons, with the exception that further vaccination will not be given and study procedures will be modified to monitor safety only.

## 13.1.5 Procedure for Accounting for Missing, Unused, and Spurious Data

All available data will be used in the analyses and there will be no imputations for missing data.

## 13.1.6 Inclusion in Analysis

All enrolled participants with any available data will be included in the analyses. All analyses will be 'as treated'.

#### 13.1.7 Interim Analysis

An interim analysis of safety outcomes will occur at the interim safety reviews as described in section 11.22. Interim safety and immunogenicity analyses are scheduled following the 4-week timepoint after the first vaccination, as detailed in section 11.22.1. The purpose of these analyses are to inform future planning and manufacture only. The results of the interim analyses will have no bearing on the remaining conduct of the study, and will therefore not compromise the integrity of the trial. The validity of the final analyses will not be affected. When performed on a subset of the trial population, the analysis will be undertaken with the caveat that the results and conclusions are subject to change once data from all participants has been analysed.

#### 14 ETHICS AND REGULATORY CONSIDERATIONS

#### 14.1 Declaration of Helsinki

The Investigator will ensure that this trial is conducted in accordance with the principles of the Declaration of Helsinki.

#### 14.2 Guidelines for Good Clinical Practice

The Investigator will ensure that this trial is conducted in accordance with relevant regulations and with Good Clinical Practice.

#### 14.3 Approvals

Following Sponsor approval, the protocol, informed consent form, participant information sheet, and required material will be submitted to an appropriate Research Ethics Committee (REC), HRA (if relevant), regulatory authorities (MHRA in the UK), and host institutions for written approval.

The Investigator will submit and, where necessary, obtain approval from the above parties for all substantial amendments to the original approved documents.

# 14.4 Transparency in Research

Prior to the recruitment of the first participant, the trial will have been registered on a publicly accessible database. Results will be uploaded to the ISRCTN Database within 12 months of the end of trial (as declared by the CI or their delegate). Where the trial has been registered on multiple public platforms, the trial information will be kept up to date during the trial, and the CI or their delegate will upload results to all those public registries within 12 months of the end of the trial declaration.

RECRef: 23/SC/0268 NIV001: A study of a new vaccine against Nipah Page 55 of 71

#### 14.5 Reporting

Once a year or on request throughout the clinical trial, the CI or their delegate will submit an Annual Progress Report to the REC, HRA (where required), host organisation, funder (where required) and Sponsor. In addition, an End of Trial notification and summary report will be submitted to the MHRA, the REC, host organisation and Sponsor.

# 14.6 Participant Confidentiality

The trial staff will ensure that the participants' anonymity is maintained. Participants will be identified only by a participant ID number on all trial documents and any electronic database (except for the participant electronic diaries where an email address will also be used). All documents will be stored securely and only accessible by trial staff and authorised personnel. The trial will comply with UK General Data Protection Regulation (GDPR) and Data Protection Act 2018, which requires data to be anonymised as soon as it is practical to do so.

Tests for Hepatitis B and C are carried out as part of the screening investigations for this trial. Hepatitis B and C are notifiable organisms listed under the UK Health Protection (Notification) Regulations 2010 and therefore must be reported to the relevant public health authority if they are suspected. Notification of infectious diseases is mandatory under UK law and participants will not be able to opt out of reporting. This will be included in the participant information sheet.

# 14.7 Participant Financial Compensation

Participants will be reimbursed £110 for their screening visit and each vaccination visit. For each of the follow up visits, participants will be reimbursed £90. Upon completion of each diary card participants will be reimbursed a further £30.

Each participant can therefore receive a maximum of:

- The first six participants; cohort 1: £1,380
- The remaining 45 participants; cohort 2: £1020

An additional £90 reimbursement will be provided for any unscheduled visit(s). The total amount of compensation for an individual participant will depend on the actual number of visits attended and whether any repeat or additional visits were necessary.

Participants will be reimbursed *pro rata* at scheduled timepoints during the study:

- The first six participants; cohort 1: Following visits 1, 4, 7 and 13
- The remaining 45 participants; cohort 2: Following visits 1, 5 and 9

Participants who attend screening but are not enrolled in the study (i.e., do not complete any further study visits) will be reimbursed following their screening visit. If a participant withdraws consent for continued participation in the trial or is withdrawn for any other reason, they will be compensated for any trial visits they attended.

RECRef: 23/SC/0268 NIV001: A study of a new vaccine against Nipah Page 56 of 71 IRAS project ID: 1007433 Virus in adults aged 18 to 55

Virus in adults aged 18 to 55 Protocol V4.0, 16 AUG 2024

# 15 QUALITY CONTROL AND QUALITY ASSURANCE PROCEDURES

#### 15.1 Investigator procedures

Approved standard operating procedures (SOPs) will be used at all clinical and laboratory sites.

#### 15.2 Risk Assessment

The trial will be conducted in accordance with the current approved protocol, GCP, relevant regulations and Standard Operating Procedures. A risk assessment and monitoring plan will be prepared before the study opens and will be reviewed as necessary over the course of the trial to reflect significant changes to the protocol or outcomes of monitoring activities. Approved and relevant SOPs will be used at all clinical and laboratory sites.

#### 15.3 Monitoring

Monitoring will be performed according to GCP by OVG. Following written SOPs, the monitors will verify that the clinical trial is conducted and data are generated, documented and reported in compliance with the protocol, GCP and the applicable regulatory requirements. Trial site(s) will provide direct access to all trial-related source data/documents and reports for the purpose of monitoring and auditing by the sponsor and inspection by local and regulatory authorities.

#### 15.4 Protocol Deviation

Any deviations from the protocol will be documented in a protocol deviation form and filed in the trial master file. Each deviation will be assessed as to its impact on volunteer safety and study conduct. Significant deviations will be listed in the end of study report.

# 15.5 Audit and Inspection

The QA at OVG manager conducts systems-based internal audits to check that trials are being conducted according to local procedures and in compliance with GCP and applicable regulations.

The Sponsor, trial site(s), and ethical committee(s) may carry out audits to ensure compliance with the protocol, GCP and appropriate regulations.

GCP inspections may also be undertaken by the MHRA to ensure compliance with protocol and the Medicines for Human Use (Clinical Trials) Regulations 2004, as amended. The Sponsor will assist in any inspections and will support the response to the MHRA as part of the inspection procedure.

#### 16 FINANCING AND INSURANCE

# 16.1 Financing

The study is funded by the Coalition for Epidemic Preparedness Innovations (CEPI).

# 16.2 Insurance

The University has a specialist insurance policy in place which would operate in the event of any participant suffering harm as a result of their involvement in the research (Newline Underwriting Management Ltd, at Lloyd's of London).

RECRef: 23/SC/0268 NIV001: A study of a new vaccine against Nipah Page 57 of 71

#### 16.3 Contractual Arrangements

Appropriate contractual arrangements will be put in place with all third parties.

#### 17 SERIOUS BREACHES

The Medicines for Human Use (Clinical Trials) Regulations contain a requirement for the notification of "serious breaches" to the MHRA within 7 days of the Sponsor becoming aware of the breach.

A serious breach is defined as "A breach of GCP or the trial protocol which is likely to affect to a significant degree

- (a) the safety or physical or mental integrity of the participants of the trial; or
- (b) the scientific value of the trial".

In the event that a serious breach is suspected, the Sponsor will be informed within one working day.

#### **18 PUBLICATION POLICY**

The Investigators will be involved in reviewing drafts of the manuscripts, abstracts, press releases and any other publications arising from the study. Data from the study may also be used as part of a thesis for a PhD or MD.

# 19 DEVELOPMENT OF A NEW PRODUCT/PROCESS OR THE GENERATION OF INTELLECTUAL PROPERTY

Ownership of IP generated by employees of the University vests in the University. The protection and exploitation of any new IP is managed by the University's technology transfer office, Oxford University Innovations.

RECRef: 23/SC/0268 NIV001: A study of a new vaccine against Nipah Page 58 of 71 IRAS project ID: 1007433 Virus in adults aged 18 to 55

# **20 ABBREVIATIONS**

Abbreviations
Acute Disseminated Encephalomyelitis
Adverse event
Adverse Events of Special Interest
Alkaline phosphatase
Alanine aminotransferase
Adverse reaction
Aspartate aminotransferase
Clinical Biomanufacturing Facility
Centre for Clinical Vaccinology and Tropical Medicine
Chimpanzee Adenovirus serotype 63
Chimpanzee Adenovirus Ox1
Chimpanzee Adenovirus Ox2
Chief Investigator
Capillary leak syndrome
Human cytomegalovirus
Case Report Form
Clinical Trial of an Investigational Medicinal Product
Disability-adjusted life years
Deoxyribonucleic acid
Data Safety Monitoring Commitee
Development Safety Update Report
Epstein Barr virus
Ebola Virus Disease
Zaire Ebolavirus
Electronic Data Capture
Enzyme linked immunosorbent assay
Enzyme linked immunospot assay
Electronic Case Report Form
European Medicines Agency
Electronic participant reported outcomes
Food and Drug Administration
Filovirus Glycoprotein
Guillain-Barre Syndrome
Good Clinical Practice
Gamma-glutamyl Transferase
Genetically modified organism
Good Manufacturing Practice
General Practitioner
Hepatitis B surface antigen
Human Chorionic Gonadotrophin
Hepatitis C virus
Hepatitis C virus antibody
Human embryonic kidney
Heparin-Induced Thrombocytopenia
Human immunodeficiency virus
Human leukocyte antigen
, ,

RECRef: 23/SC/0268 NIV001: A study of a new vaccine against Nipah Page 59 of 71

	Abbreviations
IB	Investigators Brochure
ICH	International Conference on Harmonisation
ICS	Intracellular Cytokine Staining
IFN	Interferon
IM	Intramuscular/intramuscularly
IMP	Investigational medicinal product
ISF	Investigator Site File
ITP	Immune thrombocytopaenia purpura
IU	Infectious units
IUD	Intrauterine device
IUS	Intrauterine system
JCVI	Joint Committee on Vaccination and Immunisation
LVLV	Last volunteer last visit
MERS	Middle Eastern Respiratory Syndrome
MERS-CoV	Middle Eastern Respiratory Syndrome-Related Coronavirus
MHRA	Medicines and Healthcare products Regulatory Agency
mRNA	Messenger ribonucleic acid
MVA	Modified Vaccinia Virus Ankara
NAAT	Nucleic Acid Amplification Test
NCT Number	National Clinical Trial number
NHAIS	National Health Applications and Infrastructure Services
NHP	Non-human primate
NIAID	National Institute of Allergy and Infectious Diseases
NiV	Nipah virus
NiV B	Nipah virus Bangladesh strain
NiV M	Nipah virus Malaysia strain
OUHFT	Oxford University Hospital Foundation Trust
OVC	Oxford Vaccine Centre
OVG	Oxford Vaccine Group
PBMC	Peripheral blood mononuclear cell
PCR	Polymerase Chain Reaction
PEP	Post-exposure prophylaxis
PFU	Pore forming units
PIC	Participant Identification Centres
PIS	Participant information sheet
PrEP	Pre-exposure prophylaxis
PT	Preferred terms
QP	Qualified Person
RCT	Randomised controlled trial
REC	Research Ethics Committee
RGEA	Research Governance, Ethics and Assurance (formerly Clinical Trials and
NGEA	Research Governance)
RNA	Ribonucleic acid
RSV	Respiratory syncytial virus
SAE	Serious Adverse Event
SAR	Serious Adverse Event Serious Adverse Reaction
SARS-CoV-2	Severe acute respiratory syndrome coronavirus 2
SFU	Spot forming units

RECRef: 23/SC/0268 NIV001: A study of a new vaccine against Nipah Page 60 of 71

Abbreviations		
SmPC	Summary of Product Characteristics	
SOC	System Organ Classes	
SOP	Standard Operating Procedure	
SUDV	Sudan Ebolavirus	
SUSAR	Suspected Unexpected Serious Adverse Reaction	
TMF	Trial Master File	
TOPS	The Over-Volunteering Prevention System	
TTS	Thrombosis with thrombocytopenia	
UKHSA	United Kingdom Health Security Agency	
VAERS	Vaccine Adverse Event Reporting System	
VNA	Virus neutralising assay	
νр	Viral particles	
WHO	World Health Organization	
WOCBP	Women of Childbearing Potential	

RECRef: 23/SC/0268 NIV001: A study of a new vaccine against Nipah Page 61 of 71 Virus in adults aged 18 to 55

# 23 Appendix B: Severity Grading Scales

**Table 9** Severity grading criteria for local adverse events \*erythema ≤2.5cm is an expected consequence of skin puncture and will therefore not be considered an adverse event

Adverse Event	Grade	Intensity
Erythema at injection site*	1	2.5 - 5 cm
	2	5.1 - 10 cm
	3	>10 cm
	4	Necrosis or exfoliative dermatitis

**Table 10** Severity grading criteria for local and systemic AEs. NB: A&E assessment in itself does not constitute a SAE. Refer to 11.1 for SAE definitions.

GRADE 0	None
GRADE 1	Mild: Transient or mild discomfort (< 48 hours); No interference with activity; No medical intervention/therapy required
GRADE 2	Moderate: Mild to moderate limitation in activity – some assistance may be needed; no or minimal medical intervention/therapy required
GRADE 3	Severe: Marked limitation in activity, some assistance usually required; medical intervention/therapy required.
GRADE 4	Potentially Life-threatening: requires assessment in A&E or hospitalisation

Table 11 Severity grading criteria for physical observations (applies to adults only). \*Taken after ≥10 minutes at rest \*\*When resting heart rate is between 60 – 100 beats per minute. Use clinical judgement when characterising bradycardia among some healthy subject populations, for example, conditioned athletes. \*\*\*Only if symptomatic (e.g. dizzy/ light-headed)

Vital Signs	Grade 1 (mild)	Grade 2 (moderate)	Grade 3 (severe)	Grade 4 Potentially Life threatening
Fever (oral)	38.0°C - 38.4°C	38.5°C – 38.9°C	39.0°C - 40°C	> 40°C

RECRef: 23/SC/0268 NIV001: A study of a new vaccine against Nipah Page 67 of 71

Tachycardia (bpm)*	101 - 115	116 – 130	>130	A&E visit or hospitalisation for arrhythmia
Bradycardia (bpm)**	50 – 54	45 – 49	<45	A&E visit or hospitalisation for arrhythmia
Systolic hypertension (mmHg)	141 - 150	151 – 155	≥155	A&E visit or hospitalisation for malignant hypertension
Diastolic hypertension (mmHg)	91 - 95	96 – 100	>100	A&E visit or hospitalisation for malignant hypertension
Systolic hypotension (mmHg)***	85 - 89	80 – 84	<80	A&E visit or hospitalisation for hypotensive shock
Respiratory Rate (breaths per minute)	17 - 20	21-25	>25	Intubation

 Table 12 Oxford Vaccine Group Site Specific Severity Grading Scale for Laboratory AEs

Blood Test	Unit	Grade 1	Grade 2	Grade 3	Grade 4
Albumin	g/L	31 - 28	27 - 25	≤ 24	-
Alkaline phosphate	U/L	143 - 260	261 - 390	391 - 1300	≥ 1301
ALT (female)	U/L	49 - 112	113 - 225	226 - 450	≥ 451
ALT (male)	U/L	No diffe	rence betwee	n male and fe	male
Bilirubin – (abnormal ALT/ALP)	μmol/L	23 - 26	27 - 32	33 - 37	≥ 38
Bilirubin – (normal ALT/ALP)	μmol/L	23 - 32	33 - 42	43 - 63	≥ 64
Creatinine (female)	μmol/L	No diffe	rence betwee	n male and fe	emale
Creatinine (male)	μmol/L	114 - 156	157 - 312	≥ 313	-
Eosinophils	cells/μL	0.65 - 1.50	1.51 - 5.00	≥ 5.01	-
Hemoglobin (female)	g/l	113 - 105	104 - 90	89 - 80	≤ 79
Hemoglobin (male)	g/l	125 - 115	114 - 100	99 - 85	≤ 84
Lymphocytes	cell/mm3	0.99 - 0.75	0.74 - 0.50	0.49 - 0.25	≤ 0.24
Neutrophils	cell/mm3	1.99 - 1.5	1.49 - 1	0.99 - 0.51	≤ 0.5
Platelets	cell/mm3	140 - 125	124 - 100	99 - 25	≤ 24
Potassium	mEq/L	5.4-5.5	5.6-5.7	5.8-6.8	≥ 6.9
Potassium	mEq/L	3.3 - 3.2	3.10	3 - 2.5	≤ 2.4
Sodium	mmol/L	132 - 130	129 - 128	127 - 123	≤ 122
Sodium	mmol/L	146 - 147	148-149	150-155	≥ 156
Urea	mmol/L	8.2 - 9.3	9.4 - 11.0	≥ 11.1	-
WBC	cells/μL	3.49 - 2.50	2.49 - 1.50	1.49 - 1.00	≤ 0.99
WBC	cells/μL	11.50 - 15.00	15.01 - 20.00	20.01 - 25.00	≥ 25.01

RECRef: 23/SC/0268 NIV001: A study of a new vaccine against Nipah Page 69 of 71
IRAS project ID: 1007433 Virus in adults aged 18 to 55
Protocol V4.0, 16 AUG 2024

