#### 11.12 Laboratory AEs

Severity grading for laboratory AEs are defined in Appendix B: Severity Grading Scales. All changes in laboratory values will be recorded as AEs if they are of Grade 2 severity or above. Changes of laboratory values of Grade 1 severity may be recorded as AEs if they are judged to be clinically significant by a blinded PI-delegated clinician / Investigator.

If a test result is deemed clinically significant, it may be repeated to ensure it is not a single occurrence or spurious result. If a test result remains clinically significant, the participant will be informed and advised with regards to appropriate medical care. If abnormal laboratory values are the result of pathology for which there is an overall diagnosis, then this diagnosis will be reported as one AE only.

A Grade 4 laboratory AE will be considered a SAE.

RECRef: 23/SC/0268 NIV001: A study of a new vaccine against Nipah Page 46 of 71 IRAS project ID: 1007433 Virus in adults aged 18 to 55

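### Table 12 labels six blood-count rows in cells per mm3 or μL although the thresholds work only in 10^9/L, so grading in the printed unit is wrong by a factor of 1,000; separately, Table 11 puts 155 mmHg in two grades

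*Protocol*

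**What the plan says.** Appendix B, Table 12 is the laboratory grading scale. Three of its rows carry the unit cell/mm3:

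- Platelets: "Platelets cell/mm3 140 - 125 124 - 100 99 - 25", with Grade 4 at 24 or below.
- Neutrophils: "Neutrophils cell/mm3 1.99 - 1.5 1.49 - 1 0.99 - 0.51", with Grade 4 at 0.5 or below.
- Lymphocytes: "Lymphocytes cell/mm3 0.99 - 0.75 0.74 - 0.50 0.49 - 0.25", with Grade 4 at 0.24 or below.

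Three carry the unit cells/μL:

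- Eosinophils: Grades 1 and 2 are "0.65 - 1.50 1.51 - 5.00", with Grade 3 from 5.01.
- Low white-cell count: "3.49 - 2.50 2.49 - 1.50 1.49 - 1.00", with Grade 4 at 0.99 or below.
- High white-cell count: "11.50 - 15.00 15.01 - 20.00 20.01 - 25.00", with Grade 4 from 25.01.

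None of the six rows shows a multiplier.

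Section 11.12 sends laboratory grading to Appendix B, makes recording mandatory from Grade 2, and adds: "A Grade 4 laboratory AE will be considered a SAE". Sections 11.24.1 and 11.24.2 use Grade 3 laboratory events, lymphopenia excepted, in the group and individual holding rules.

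In Table 11, which section 11.10 uses to grade vital signs, the row beginning "Systolic hypertension (mmHg" gives Grade 2 as 151 to 155 and Grade 3 as 155 and above.

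**The concern.** A platelet threshold of 140 cells per mm3, or a lymphocyte threshold of a quarter of one cell per mm3, cannot be a real boundary. The unit column and the numbers therefore disagree on six rows. Elsewhere this would be a typographical matter. Here the table decides which results become recorded adverse events, which become SAEs, and which count towards a hold in a first-in-human trial. Full blood counts are planned at 12 visits for each of 6 participants in cohort 1 and at 8 visits for each of 45 in cohort 2, not counting screening. That is 6 × 12 + 45 × 8 = 432 samples to be graded from these rows.

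The systolic overlap is a smaller defect of another kind: one blood pressure value has two grades.

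**Working it through.** The protocol gives no derived figure to reproduce here. The check is one of units and grade boundaries.

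**Unit conversion.** 1 mm3 = 1 μL, so both printed labels are the same scale. 1 L = 10^6 μL, so 10^9/L = 10^9 / 10^6 = 10^3 per μL. The printed and evident units differ by exactly 1,000.

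**Inputs.** Thresholds are from Table 12. The healthy ranges below are assumptions, since the protocol gives none. Each row was applied to the count per μL as printed, and again after dividing the count by 1,000.

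| Row | Assumed healthy range (per μL) | Grade in printed unit | Grade in 10^9/L |
|---|---|---|---|
| White cells | 4,000 to 11,000 | 4 (high) | none |
| Eosinophils | 20 to 500 | 3 | none |
| Neutrophils | 2,000 to 7,500 | none | none |
| Lymphocytes | 1,000 to 4,000 | none | none |
| Platelets | 150,000 to 400,000 | none | none |

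**Single values, also assumed.**

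- White cells 6,000/μL. Printed unit: 6,000 ≥ 25.01, so Grade 4, and an SAE under section 11.12. Divided by 1,000: 6.0 lies between 3.49 and 11.50, so no grade.
- Platelets 20,000/mm3. Printed unit: 20,000 > 140, so no grade. Divided by 1,000: 20 ≤ 24, so Grade 4.
- Neutrophils 400/mm3. Printed unit: 400 > 1.99, so no grade. Divided by 1,000: 0.4 ≤ 0.5, so Grade 4.

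**Sensitivity to the assumed ranges.** Slight. In the printed unit any white-cell count from 25.01/μL (about 0.025 x10^9/L) is Grade 4. Platelets receive a grade only at 140/mm3 or below (0.14 x10^9/L). No plausible choice of healthy range alters the result.

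**Systolic bands.** 154 falls in Grade 2 only, 155 in Grades 2 and 3, and 156 in Grade 3 only. The diastolic row beside it (96 to 100, then above 100) has no overlap.

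**The case against.** The strongest reply is that this is a label slip and the thresholds themselves are sound. Read in 10^9/L the numbers grade sensibly, and a laboratory result already in that unit, compared directly with the printed number, gets the intended grade. There is one recruiting site, the scale is described as specific to it, and an accredited local laboratory runs the tests. Sections 11.6, 11.12 and 11.23 provide for assessment of clinical significance and for repeat tests. A literal reading would also expose itself at once, because nearly every white-cell count would be an SAE. All of this stands, and it limits the practical risk. It does not make the printed unit correct: the protocol does not state the laboratory's reporting unit, and no other section corrects the table. A multiplier lost in typesetting is conceivable, but it would have to be missing from six rows in two unit styles.

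A reader might infer more than the document supports:

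- That any grading programmed from the table must be wrong. It goes wrong only if results are taken in, or converted to, the printed unit.
- That everyone would meet every high-count grade and no one could meet a low-count grade. In the printed unit a white-cell count of 6,000/μL meets Grade 4 alone, a zero eosinophil count meets no grade, and the low grades are out of reach only in practice.
- That Table 12 defines primary outcome (d). Section 6.1 names abnormal safety laboratory measures without citing the table; the link runs through sections 11.5 and 11.12.
- That detection of thrombocytopenia as an AESI depends on the table. Section 11.2 lists it by name with no grade threshold.
- That the label alone could trigger a hold. The Grade 3 laboratory rules also need judged relatedness and persistence beyond 48 hours, and a Grade 4 result reaching the group rule as an SAE would still have to be judged related.

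**Conclusion.** The unit labels on six rows of Table 12 are wrong as written, by a factor of exactly 1,000, and the thresholds are coherent in 10^9/L. Applied literally, or through code that converts to the printed unit, the table would grade ordinary white-cell counts as SAEs and leave very low platelet and neutrophil counts ungraded. Where results are reported and compared in 10^9/L, grading is as intended, so nothing here shows that any result has been misgraded. The example counts are assumptions, but the conclusion does not turn on them. Haemoglobin and biochemistry rows are unaffected. The correction is worth making because the table is operative for event recording, laboratory SAEs and holding rules.

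The double grade at 155 mmHg is real but minor: one value in one row, on which no laboratory rule depends.

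**What to change.** Change the unit column for eosinophils, lymphocytes, neutrophils, platelets and both white-cell rows to x10^9/L. No threshold or grade changes. Confirm which unit the laboratory reports and which unit the eCRF and analysis grading use, and document the answer. If any grading was done in the printed unit, regrade those results.

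Separately, reconcile the two systolic cells in Table 11 so that each value has one grade. The choice of boundary belongs to the sponsor.

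The cost is a short table correction and a check of the grading rules. It is not quite free: version 4.0 is dated August 2024 and the planned trial period ends in Q4 2024, so an amendment would come late. The documented confirmation of the grading unit is the part that protects the results and should be done whenever the table itself is corrected.
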